5.6.12	Other Safety Assessments.....	52
5.6.12.1	Presentations.....	52
6	INTERIM ANALYSIS.....	52
7	REFERENCES.....	53
8	APPENDICES.....	54
	Appendix A Time windows for Module 1 – Efficacy assessments.....	54

LIST OF ABBREVIATIONS

Abbreviation or Specialized Term	Definition
3L	Third-line
AE	Adverse event
AESI	Adverse event of special interest
ALT	Alanine aminotransferase
AST	Aspartate aminotransferase
ATC	Anatomical Therapeutical Chemical
BMI	Body mass index
BOR	Best Overall Response
BSR	Baseline scaled ratio
BV	Brentuximab vedotin
cHL	Classical Hodgkin Lymphoma
CI	Confidence interval
COVID-19	Coronavirus disease 2019
CR	Complete response
CSP	Clinical Study Protocol
CSR	Clinical Study Report
CTCAE	Common Terminology Criteria for Adverse Events
CV	Coefficient of variation
DCO	Data cut-off
DoR	Duration of response
ECG	Electrocardiogram
ECOG	Eastern Cooperative Oncology Group
eCRF	Electronic case report form
FAS	Full analysis set
gCV	Geometric coefficient of variation
gMean	Geometric mean
gSD	Geometric standard deviation
IP	Investigational Product
IPD	Important protocol deviation
IPI	International Prognostic Index
ITT	Intent-to-Treat
IV	Intravenous

Abbreviation or Specialized Term	Definition
LLOQ	Lower limit of quantification
MedDRA	Medical Dictionary for Regulatory Activities
NA	Not applicable
NC	Not calculable
NE	Not evaluable
NK	Natural killer
NKTCL	Natural killer T-cell lymphoma
NS	No sample
OAE	Other significant adverse event
ORR	Objective response rate
OS	Overall survival
PD	Progressive disease
PD1	Anti-programmed cell death-1
PFS	Progression-free survival
PK	Pharmacokinetics
PR	Partial response
PT	Preferred term
PTCL	Peripheral T-cell Lymphoma
r/r	Relapsed/refractory
RDI	Relative dose intensity
RP2D	Recommended phase 2 dose
SAE	Serious adverse event
SAP	Statistical Analysis Plan
SD	Stable disease
SOC	System Organ Class
Std Dev	Standard deviation
TEAE	Treatment emergent adverse event
TFL	Tables, figures and listings
TLS	Tumour lysis syndrome
ULN	Upper limit of normal
WHO	World Health Organisation
WHODrug	World Health Organisation Drug Dictionary

AMENDMENT HISTORY

CATEGORY Change refers to:	Date	Description of change	In line with CSP?	Rationale
N/A	15-Mar-2022	Initial approved SAP	N/A	N/A
Data presentation	20-Nov-2023	Added the interim response evaluable set in Section 4.2.2	N/A	This analysis set is currently not planned to be used for any outputs to be presented in the CSR. This analysis set will only be used for presentation in conferences and publications.
Data presentation	20-Nov-2023	Mention that SAP is for conference and publication purposes as well in Section 1	N/A	Details added to mention that this SAP is not only to describe CSR analyses, but also analyses performed for conferences and publications.
Data presentation	20-Nov-2023	Swimmer plot for response assessment added in Section 5.2.1.2	Yes	Visual representation of disease assessment results over time added for better understanding of the results.
Derivation of secondary endpoint(s)	20-Nov-2023	Added formula to derive QTcB in Section 5.6.10.1	Yes	QTcB was required for presentation per Version 1.0 of this document, but the formula was never provided.
Derivation of secondary endpoint(s)	20-Nov-2023	Clarified that duration of follow-up in overall survival should be derived for all participants and not just for censored participants in Section 5.2.5.2	Yes	Clarification provided to derivation provided in Version 1.0 of this document.
Derivation of secondary endpoint(s)	20-Nov-2023	Updated TLS monitoring derivations in Section 5.6.9	Yes	Consistency of text within the compound.
Other	20-Nov-2023	Removed imputation for missing best percentage change	Yes	Imputation does not make clinically sense.

CATEGORY Change refers to:	Date	Description of change	In line with CSP?	Rationale
		in target lesion in Section 5.2.1.3.1		
Data presentation	20-Nov-2023	Removed requirement to present ramp-up dosing in disposition Section 5.1.1.2	Yes	Not required per protocol and not adding any value in presentations.
Data presentation	20-Nov-2023	Update derivation of actual exposure in Section 5.6.1	Yes	Updated to be in line with standards as current derivations caused actual exposure to be longer than intended exposure.
Data presentation	20-Nov-2023	Update derivation of RDI and dose delays in Section 5.6.1 to account for windows around dosing	Yes	Added a statement that RDI should consider the ± 2 days window around doses. Dose delays were determined using 7 days between doses. Per a dosing window of ± 2 days around doses the calculation is updated to use 9 days instead of 7 days.
Data presentation	20-Nov-2023	Clarified that where we have missing post-baseline target lesions that these should not be presented in figures or summaries in Section 5.2.1.3	Yes	Missing target lesions underrepresent the target lesion sizes and changes at post-baseline timepoints.
Data presentation	20-Nov-2023	Clarified that highest ATC level should be used in summaries in Section 5.1.8.2	Yes	Clarification on what should be presented in summaries.
N/A	20-Nov-2023	Approved SAP Version 2.0	N/A	N/A
Data presentation	12-Dec-2023	Removed timepoint window derivations for safety endpoints from Section 4.1.3.2 .	Yes	Due to the schedule of assessments in this study, it makes more sense to present results as recorded in the database as reassessment of

CATEGORY Change refers to:	Date	Description of change	In line with CSP?	Rationale
				visits caused confusion in interpretation of results.
N/A	12-Dec-2023	Approved SAP Version 3.0	N/A	N/A

1 INTRODUCTION

The purpose of this document is to give details for the statistical analysis of study D8231C00001 supporting the clinical study report (CSR). Details provided in this document will also support the statistical analysis for conferences and publications. The reader is referred to the clinical study protocol (CSP) version 2 (dated 09 Sep 2021) and the electronic case report form (eCRF) for details of study conduct and data collection. While CSP version 3 (dated 16 Mar 2023) was released for use in some countries, it had no impact on the statistical analyses. The Statistical Analysis Plan (SAP) should not be read in isolation but in conjunction with the CSP.

2 STUDY DETAILS

The overarching primary hypothesis for this study is: AZD4573 will demonstrate anti-tumour efficacy, as monotherapy or in combination with other anti-cancer agents, in participants with either relapsed/refractory (r/r) Peripheral T-cell Lymphoma (PTCL) or r/r classical Hodgkin Lymphoma (cHL).

2.1 Module 1

2.1.1 Study Objectives

Table 1 Objectives and Endpoints – Module 1

Type	Objectives	Endpoints
Primary		
Efficacy	To assess the efficacy of AZD4573 by evaluation of objective response rate.	
 • Endpoint based on Lugano response criteria for malignant lymphoma (Cheson et al 2014) 
 – ORR, defined as the proportion of participants who have a tumour response (CR or PR)^a
Secondary		
Efficacy	To assess efficacy of AZD4573 by evaluation of tumour response and OS.	
 • Endpoints based on Lugano response criteria for malignant lymphoma (Cheson et al 2014) 
 – CR rate – DoR – PFS • OS

Table 1 Objectives and Endpoints – Module 1

Type	Objectives	Endpoints
Safety	To assess the safety and tolerability of AZD4573.	
Adverse events, laboratory data, vital signs, and ECG changes.
 
Assessments related to AEs cover:
 
 • Occurrence/frequency • Relationship to IP as assessed by investigator • CTCAE grade • SAEs • Death • AEs leading to discontinuation of IP • AEs leading to dose modifications • AESIs
PK	To assess the plasma PK of AZD4573.	
 • Plasma concentrations and derived PK parameters for AZD4573
Exploratory		
PD	To assess the pharmacodynamics of AZD4573.	
 • CCI [REDACTED]
CCI	CCI [REDACTED]	
 • CCI [REDACTED]
CCI	CCI [REDACTED]	
 • CCI [REDACTED]

Table 1 Objectives and Endpoints – Module 1

Type	Objectives	Endpoints
Genetics	To collect and store CCI sample, for future exploratory research CCI	• CCI

^a By investigator assessment; however, if preliminary results suggest a major advance over available therapy, AstraZeneca will consult with relevant Health Authorities to agree on modifications to the protocol and will conduct blinded independent central review of ORR.

Abbreviations: AE, adverse event; CCI; CR, complete response; CTCAE, Common Terminology Criteria for Adverse Events; DoR, duration of response; ECG, electrocardiogram; IP, investigational product; CCI; CCI; MTD, maximum tolerated dose; ORR, objective response rate; OS, overall survival; CCI; CCI; PD, pharmacodynamics; PFS, progression-free survival; PK, pharmacokinetics; PR, partial response; CCI SAE, serious adverse event; TTR, time to response.

2.1.2 Study Design

[figure not shown]
Module 1 will assess the efficacy of AZD4573 as a monotherapy in r/r PTCL and r/r cHL populations. Module 1 is non-randomised and will consist of 2 r/r PTCL cohorts (non-natural killer [NK] PTCL and natural killer T-cell lymphoma [NKTCL]) and one r/r cHL cohort.

During the first cycle per the protocol, participants will normally receive a single dose of AZD4573 once weekly, beginning with intra-participant ramp-up doses of 6 mg and 9 mg in Week 1 and Week 2, respectively. This is then followed by the target dose level of 12 mg for each of Weeks 3 to 5. It should be noted, however, that it may take more than 5 weeks to complete 3 AZD4573 dose weeks at target level, due to missed dose weeks and/or by repeating lower (ramp-up) doses of AZD4573. For the purposes of analysis defined in this SAP, Cycle 1 is defined as having received 5 doses of AZD4573 (regardless of dose level).

Each cycle beyond Cycle 1 will be 3 weeks in length and participants are planned to receive 12 mg infusions of AZD4573 once weekly until progression.

The dosing regimen for Module 1 is presented in [Figure 1](#).

Figure 1 Module 1 AZD4573 Monotherapy Dosing Regimen in PTCL and cHL including Intra-Participant Dose Ramp-Up

3 CHANGES TO PROTOCOL PLANNED ANALYSIS

The CSP defines Cycle 1 as having a duration of 5 weeks. Section 2.1.2 of this SAP clarifies that Cycle 1 will only be considered completed once the participant has received 5 doses of AZD4573 (at any dose level).

Section 10.9.3 of the CSP defines the safety set as all participants who receive at least one dose of investigational product (IP) (study intervention). Participants who are exposed to any amount of IP, may have safety events, even if the full dose were not received (eg, dose interruption). Therefore, the safety population definition is updated to include all participants who received any amount of IP (Section 4.2.2).

A survival sweep for the purpose of analysing overall survival (OS) is currently not included in the CSP but is included in this version of the SAP (Section 5.2.5).

4 DATA ANALYSIS CONSIDERATIONS

4.1 Core

4.1.1 Timing of Analyses

The timing of analyses is specific to each module and are discussed separately for each module.

- Module 1: Section 4.2.1

4.1.2 Analysis Populations

The analysis populations are specific to each module and are discussed separately for each module.

- Module 1: Section [4.2.2](#)

4.1.3 General Considerations

Unless stated otherwise, each module and cohort will be analysed separately. Data will be presented by cohort.

The general principles described below will be followed throughout the study:

- Continuous endpoints will be summarised by the number of observations, mean, standard deviation (Std Dev), median, upper and lower quartiles (as applicable), minimum, and maximum. For data that requires log-transformation, it is more appropriate to present geometric mean (gMean), coefficient of variation (CV), median, minimum, and maximum. Categorical endpoints will be summarised by frequency counts and percentages for each category.
- Unless otherwise stated, percentages will be calculated out of the analysis set total, by cohort as appropriate. Percentages will not be presented for zero counts.
- For continuous data (except for pharmacokinetics [PK]), descriptive summary statistics (mean, median, quartiles, Std Dev, standard error, confidence intervals [CIs]) will be rounded to one additional decimal place compared to the original data. Minimum and maximum will be displayed with the same accuracy as the original data. Decimal precision for PK is described in Section [5.4.2](#).
- For categorical data, percentages will be rounded to one decimal place.
- Time to event variables will be presented using the Kaplan-Meier methodology where appropriate, including median time calculated from the Kaplan-Meier curves.
- For summaries at the participant level, all values will be included, regardless of whether they appear in a corresponding timepoint-based summary.
- SAS[®] version 9.4 (as a minimum) will be used for analyses presented in the CSR. PK parameters will be calculated using Phoenix[®] WinNonlin[®] Version 8.1 (as a minimum).

4.1.3.1 General Study Level Definitions

Baseline is the last non-missing value obtained prior to the first dose/administration of any IP and any information taken after first dose/administration of IP is regarded as post-baseline information. If 2 timepoints are equally eligible to assess participant status at baseline (eg, screening and baseline assessments both on the same date prior to first dose/administration

with no washout or other intervention in the screening period), the average is taken as the baseline value. For non-numeric laboratory tests (ie, some of the urinalysis parameters) where taking an average is not possible then the best value is taken as baseline as this is the most conservative. In the scenario where there are 2 assessments on Day 1 prior to first dose, one with time recorded and the other without time recorded, the one with time recorded is selected as baseline. Where safety data are summarised over time, study day is calculated in relation to date of first intervention of IP. For assessments on the day of first dose where time is not captured, a nominal pre-dose indicator, if available, serves as sufficient evidence that the assessment occurred prior to first dose. Assessments on the day of the first dose where neither time nor a nominal pre-dose indicator are captured is considered prior to the first dose. If no value exists before the first dose/administration, then the baseline value is treated as missing.

In all summaries, change from baseline variables will be calculated as the post-baseline value minus the value at baseline. The percentage change from baseline will be calculated as $(\text{post-baseline value} - \text{baseline value}) / \text{baseline value} \times 100$. For any endpoint subjected to log transformation, the change from baseline calculated and summarised on the log scale are back-transformed and presented as a ‘baseline scaled ratio’ (BSR). Percentage change is then calculated as $(\text{BSR} - 1) \times 100$.

Study Day 1 is defined as the date of the first dose of IP (Cycle 1 Day 1). For timepoints (or events) that occur on or after first dose of IP, Study Day is derived as $(\text{date of timepoint} [\text{event}] - \text{date of first dose of IP} + 1)$. For timepoints (or events) that occur prior to first dose, Study Day is defined as $(\text{date of timepoint} [\text{event}] - \text{day of first dose of IP})$. There is no Day 0 defined for this study.

For listings (such as adverse events [AEs]) that include the derivation of “days since last dose”, this is defined as $(\text{event date} - \text{date of last dose})$ where “date of last dose” is defined as the date of dosing immediately preceding the event occurrence. Events that occur on the same day as the last dose of IP will therefore be described as occurring 0 days from last dose of IP.

Study periods for the purpose of safety summaries will be defined as follows:

- Pre-treatment: Any result prior to first dose of IP.
- On-treatment: Any result from first dose of IP up to 30 days after last dose of IP, and prior to start of any subsequent cancer therapy.
- Follow-up: Any result after 30 days after last dose of IP, or after start of any subsequent cancer therapy.

For the purpose of summarising safety data assessed at timepoints, in addition to baseline data, only on-treatment data (as defined above) will be included in the summary tables.

Naming conventions of timepoints for inclusion in summary tables will be defined separately for each module.

- Module 1: Section [4.2.3.1](#)

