^c Results of safety laboratory testing (haematology and clinical chemistry at a minimum) must be available within 72 hours prior to dosing and must be reviewed by the investigator prior to each administration of AZD4573. To initiate Cycle 1 and subsequent cycles, haematology and chemistry criteria in inclusion criteria 10, 13, and 14 shall be met. In addition, during AZD4573 treatment, dose modification and discontinuation guidelines are provided in Section 10.6.1.

^d Mandatory exploratory CCI analysis will be performed any time a bone marrow analysis is performed.

^e The follow-up visit will be performed 30 days (± 7 days) after the last dose of all study drug. Disease assessments will be repeated at this visit if they have not been performed within 9 weeks if the participant discontinued before Week 26, or 12 weeks if the participant discontinued after Week 26.

Abbreviations: ACTH, adrenocorticotrophic hormone; ECG, electrocardiogram; ECHO, echocardiogram; ECOG, Eastern Cooperative Oncology Group; FU, follow-up; IgA, immunoglobulin A; IgG, immunoglobulin G; IgM, immunoglobulin M; IV, intravenous; LTFU, long-term follow-up; MUGA, multigated acquisition; PK, pharmacokinetic; PTCL, peripheral T-cell lymphoma; SoC, standard of care; SOI, start of infusion; TLS, tumour lysis syndrome; TSH, thyroid stimulating hormone; WOCBP, women of childbearing potential.

10.2 Introduction – Module 1

Module 1 of this study will evaluate the efficacy, safety, and tolerability of AZD4573 monotherapy in participants with r/r PTCL or r/r cHL. For an overview of the study design see [Figure 5](#).

10.3 Objectives and Endpoints – Module 1

Type	Objectives	Endpoints
Primary		
Efficacy	To assess the efficacy of AZD4573 by evaluation of objective response rate.	
Endpoint based on Lugano response criteria for malignant lymphoma (Cheson et al 2014):
– ORR, defined as the proportion of participants who have a tumour response (CR and PR)^a
Secondary		
Efficacy	To assess efficacy of AZD4573 by evaluation of tumour response and OS.	
Endpoints based on Lugano response criteria for malignant lymphoma (Cheson et al 2014):
– CR rate– DoR– PFSOS

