5.6.4.2 Presentations

The absolute values and change in each laboratory parameter from baseline to each post-baseline timepoint will be summarised graphically in box plots.

Laboratory abnormalities occurring during the on-treatment period to the last assessment on treatment will be presented. Worst toxicity grade, rates of grade 3-4 toxicity, and grade shifts of 2 or more from baseline to the maximum grade will be presented. Summaries indicating hyper- and hypo- directionality of change will be produced, where appropriate. Laboratory parameters that cannot be graded via NCI CTCAE will be summarised with frequencies of post-baseline laboratory values categorized as low (L), normal (N), or high (H) using laboratory normal ranges compared to baseline.

Listings will be provided for all laboratory results.

Liver Function Parameters

Number and percentage of participants with elevated post-baseline ALT, AST, or Total Bilirubin will be tabulated.

For participants with “Potential Hy’s law”, the change in the following laboratory parameters from baseline to each post-baseline timepoint will be summarised: ALT, AST, alkaline phosphatase, glutamate dehydrogenase, lactate dehydrogenase, gamma-glutamyl transferase, and international normalised ratio. Individual participant data for these laboratory parameters will be listed as well.

Plots for both maximum on-treatment ALT and AST versus the maximum on-treatment bilirubin (expressed as multiples of their upper limit of normal [ULN] reference range) will be produced, with reference lines at 3 x ULN for ALT and AST and 2 x ULN for total bilirubin.

Liver biochemistry test results over time for participants with elevated ALT or AST (≥ 3 x ULN) and elevated bilirubin (≥ 2 x ULN) regardless of whether or not these elevations coincide, or ALT or AST ≥ 5 x ULN will be plotted.

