5.6.6.2 Presentations

Vital signs will be assessed at baseline and throughout the study. Vital signs will be summarised by study timepoint including descriptive statistics for the value of the parameters and the changes from baseline.

Absolute values and change from baseline for vital signs data at each timepoint will be presented using box plots.

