5.6.7 Weight

5.6.7.1 Presentations

Weight will be assessed at baseline and throughout the study. Weight will be summarised by study timepoint including descriptive statistics for the value and changes from baseline.

Absolute values and change from baseline for weight at each timepoint will be presented using box plots.

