5.6.10.2 Presentations

ECG parameters will be summarised using descriptive statistics by timepoint and change from baseline for each post-baseline timepoint. Absolute values and change from baseline for ECG data at each timepoint will be presented using boxplots.

The number and percentage of participants having notable ECG interval values on intervention will be summarised.

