5.6.12 Other Safety Assessments

5.6.12.1 Presentations

Serum immunoglobulins (IgA, IgM, IgG) will be listed and summarised descriptively. Absolute values and change from baseline values at each timepoint will be presented.

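### The SAP's day-30 cut omits protocol-compliant 30-day follow-up visits on days 31 to 37 from the by-timepoint safety tables

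*SAP*

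**What the plan says.** SAP 4.1.3.1 splits safety data into three periods. On-treatment is "Any result from first dose of IP up to 30 days after last dose of IP", provided that no subsequent cancer therapy has started. Anything later is classed as Follow-up. For safety data assessed at timepoints, the section then states that, in addition to baseline, "only on-treatment data (as defined above) will be included in the summary tables".

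Protocol Table 9, footnote e (Section 10.1.2) places the follow-up visit at 30 days, with a window of 7 days either way, "after the last dose of all study drug". Blood pressure, pulse and weight (protocol 10.8.2.3), ECG (10.8.2.4) and serum immunoglobulins (10.8.2.6) are all scheduled at that visit.

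The SAP plans by-timepoint summaries of each:

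- SAP 5.6.6.2: "Vital signs will be summarised by study timepoint including descriptive statistics for the value of the parameters".
- SAP 5.6.7.1: "Weight will be summarised by study timepoint including descriptive statistics for the value and changes from baseline".
- SAP 5.6.10.2: "ECG parameters will be summarised using descriptive statistics by timepoint and change from baseline for each post-baseline timepoint".
- SAP 5.6.12.1, for immunoglobulins: "Absolute values and change from baseline values at each timepoint will be presented".

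**The concern.** The two documents draw the line for one visit in different places. The protocol treats a visit on day 34 as on time. The SAP treats its results as Follow-up data and keeps them out of the tables. Whether a participant appears in the 30-day follow-up row then depends on the appointment date within a permitted window, and a reader of the table would not know this.

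Safety is a secondary objective, and this is the scheduled safety visit after treatment has stopped. Tables are presented by cohort with about 21 response-evaluable participants planned in each, so a few omitted visits would be noticeable. Immunoglobulins are the clearest case, because they are sampled rarely and some participants have no other scheduled sample after baseline.

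**Working it through.** The plan states no figure for this, so the check is a day count and a reading of the rules side by side.

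**Inputs.** On-treatment limit: day 30 after last dose (SAP 4.1.3.1). Visit window: 30 ± 7 days after last dose (protocol Table 9, footnote e). Cycle 1 of 5 weeks and later cycles of 3 weeks (protocol 10.4.1). Immunoglobulin samples at screening, before dosing on Day 1 of Cycles 3, 6, 9 and 13, every 6 months thereafter, and at the 30-day visit (protocol 10.8.2.6).

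**Day count.**

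- Permitted days: 30 − 7 = 23 to 30 + 7 = 37, so 37 − 23 + 1 = 15 days.
- Kept by the SAP: days 23 to 30, so 30 − 23 + 1 = 8 days.
- Omitted: days 31 to 37, so 37 − 31 + 1 = 7 days.
- Share of permitted days omitted: 7/15 = 46.7%.

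**Does another SAP rule bring the visit back?**

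- SAP 4.1.3.2 applies no windowing to safety results and presents them as the database records them. SAP 4.2.3.1 takes non-efficacy timepoint names from the database. Both settle which label a result carries, not whether it enters the table.
- SAP 4.1.3 includes all values in participant-level summaries, but it separates these from timepoint-based summaries.
- SAP 4.1.3.3 keeps unscheduled results out of by-timepoint summaries, so an extra sample cannot fill the gap.

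No exception for the 30-day visit appears elsewhere.

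**Immunoglobulins.** Cycles 1 and 2 take 5 + 3 = 8 weeks = 56 days, so Cycle 3 Day 1 is nominally day 57, and later if doses are missed. A participant who stops before then has the 30-day visit as the only scheduled sample after baseline. If that visit falls on days 31 to 37, the table holds no scheduled post-baseline value for that participant.

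**Weight of one visit.** If 21 participants in a cohort attended, each omitted visit would remove 1/21 = 4.8% of the row.

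**After the change.** With the nominal visit admitted through day 37, 15 of 15 permitted days are kept and none is omitted.

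**The case against.** The best defence is that the 30-day limit is an explicit choice. SAP 4.1.3.1 names the periods, and SAP 5.6.2.1 uses the same 30 days for treatment-emergent adverse events, so events and measurements share one boundary. The values are not lost: protocol 9.4.3 has vital signs, ECG and laboratory values listed individually, and SAP 5.6.12.1 lists immunoglobulins. The visit is aimed at day 30, so few visits may fall late. Results after subsequent therapy are excluded in any case. All of this stands, and it keeps the point small. It does not explain why one scheduled visit should be split within its own window, and a listing does not complete a partly filled table row.

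Four stronger readings are tempting, but the documents do not support them:

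- **That the laboratory and urinalysis summaries are wrong too.** SAP 5.6.4.2 says "Laboratory abnormalities occurring during the on-treatment period to the last assessment on treatment will be presented", and SAP 5.6.5.2 uses the worst on-treatment urinalysis result. These are one-per-participant summaries, and the all-values rule in SAP 4.1.3 may already admit later results. If it does not, leaving Follow-up values out of an on-treatment worst-grade table is no defect. Adding them would break alignment with the adverse-event limit: a laboratory abnormality on day 34 would count as on-treatment, while an adverse event starting that day would not be treatment-emergent.
- **That 47% of visits are lost.** That figure is a share of calendar days. The documents give no distribution of visit dates.
- **That the row is biased.** Nothing in the documents links visit day to outcome. With the stated half-life of 4 to 7 hours (protocol 6.5), even day 23 is 23 × 24/7 = 78.9 half-lives after last dose at the longer value, so exposure gives no reason for early and late visits to differ. The demonstrable harm is a smaller row with undeclared membership.
- **That protocol 8.2.1 adds to the problem**, because it counts the visit from permanent discontinuation. It also points to the schedule of activities, whose footnote counts from last dose. This is a separate wording question and does not support the point.

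**Conclusion.** The mismatch is real and minor. Followed as written, the SAP omits compliant 30-day follow-up visits on days 31 to 37 from four sets of by-timepoint tables: vital signs, weight, ECG and immunoglobulins. The size is 7 of 15 permitted days; as a share of actual visits it is unknown, between 0% and 100%. A participant who stops before Cycle 3 Day 1 and is seen in that week has no scheduled post-baseline immunoglobulin value in the table, although the value is listed.

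This rests on counting the visit from last dose, as in Table 9, and on reading the SAP rule as covering tables. Its reach to box plots is not explicit, so figures are left out. No efficacy analysis is affected, and the 30-day limit for treatment-emergent adverse events is not in question.

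**What to change.** Add one sentence to SAP 4.1.3.1: results recorded in the database as the 30-day follow-up visit, taken within the protocol window (through day 37 after last dose) and before subsequent anticancer therapy, are included under that nominal visit in the by-timepoint safety tables.

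Leave unchanged the on-treatment definition, the on-treatment worst-grade laboratory and urinalysis summaries, and the 30-day treatment-emergent limit.

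The cost is one sentence and no new data. The downside is small: a few values taken 31 to 37 days after last dose enter tables otherwise limited to 30 days, but under a visit name that tells the reader what they are.
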